9. SAFETY ASSESSMENTS

The following variables will be used to describe the safety of the two procedures:

During procedure for surfactant administration

- Number and percentage of neonates with AEs starting during overall procedure for surfactant administration;
- Number and percentage of neonates with AEs starting during overall procedure for surfactant administration judged related to the procedure;
- Number of AEs occurring during overall procedure for surfactant administration requiring either oxygen alone or an increase in FiO₂ without the need for escalation of invasive or non-invasive ventilator support;
- Number of AEs starting during overall procedure for surfactant administration requiring administration of manual (bag and mask) pressure positive ventilation and related duration of ventilation (non- invasive ventilation);
- Number of AEs starting during overall procedures for surfactant administration requiring endotracheal intubation and related duration of intubation (invasive ventilation);
- Number of AEs starting during overall procedures for surfactant administration requiring circulatory support including administration of crystalloids;
- Number of AEs starting during overall procedures for surfactant administration requiring cardiopulmonary resuscitation including administration of cardiac massage or adrenaline.

After first administration

- Number and percentage of neonates with failed 1st attempt to insert the CHF6440/ETT;
- Number of attempts to the first successful insertion;
- Number of device misallocation (esophageal insertion);
- Number of maneuvers discontinued due to neonate's severe destabilization;
- Duration of the whole procedure (starting from the insertion of laryngoscope up to the removal of the catheter or ETT);
- Duration of surfactant administration (min);
- Heart rate (HR) and respiratory rate (RR) (0, 5, 15 and 30 min, 1 hour, 6 and 12 hours after administration);
- Systolic, diastolic, and mean blood pressure (SBP/DBP/ MBP) (15 and 30 min, 1 hour, 6 and 12 hours after administration);
- Premature Infant Pain Profile (PIPP) score [26] (end of surfactant administration).

During the study

- AEs, including incidence of major neonatal complications of prematurity (listed in [APPENDIX III](#)) and adverse drug reactions (ADRs);
- Blood pressure (SBP, DBP, MBP) at 24, 48, 72, 120 hours post-administration;

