- Heart Rate (HR) and respiratory rate (RR), at 24, 48, 72, 120 hours post-administration and 28 PNA, 36 weeks PMA, discharge home or 40 weeks PMA whichever comes first;
- Incidence of BPD at 36 weeks PMA;
- Death/BPD incidence at 36 weeks PMA, defined as the incidence of the neonates who are dead or alive but with a diagnosis of BPD at the time of assessment (i.e. 36 weeks PMA);
- Mortality at Day 28 PNA and 36 weeks PMA;
- Oxygen use (alone and/or during invasive and non-invasive ventilation) at Day 28 PNA and 36 weeks PMA;
- Weight, OFC and length at discharge home or 40 weeks PMA;
- Feeding and hearing status at discharge home or 40 weeks PMA, whichever comes first;
- Incidence of major neonatal morbidities at discharge home or 40 weeks PMA, whichever comes first;
- Neonates needing invasive ventilation or non-invasive respiratory support at discharge home or 40 weeks PMA;
- Neonates needing respiratory medications at discharge home or 40 weeks PMA.

24 months (± 3 months) corrected age

(This stand-alone assessment will be analyzed and reported separately from the main phase)

- Health status questionnaire, including:
 - ✓ Bayley Scales of Infant Development (cognitive and language scores);
 - ✓ Feeding method: spoon, nasogastric tube or gastrostomy;
 - ✓ Cerebral palsy evaluation;
 - ✓ Seizure evaluation;
 - ✓ Vision, hearing and communication evaluation;
 - ✓ Clinical assessment of respiratory conditions and morbidity;
 - ✓ Vital signs (SBP/DBP/MBP, HR, RR);
 - ✓ Growth assessment (Weight, OFC and length).

10. ADVERSE EVENTS REPORTING**10.1. Definitions**

An **Adverse Event** is “any untoward medical occurrence in a subject or clinical trial subject administered a medicinal product and which does not necessarily have a causal relationship with this treatment”.

An adverse event can therefore be any unfavorable and unintended sign (including abnormal laboratory finding), symptom, or disease temporally associated with the use of an investigational product, whether or not considered related to the investigational product.

An **Adverse Drug Reaction** is an “untoward and unintended responses to an investigational medicinal product related to any dose administered”.

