10.4. Causality Assessment

The following “binary” decision choice will be used by the Investigator to describe the causality assessment with the study medication/device/procedure:

- Reasonable possibility of a relatedness with study medication/device/procedure
- No reasonable possibility of relatedness with study medication/device/procedure

Each AE will be evaluated for its relationship with the study drug (Poractant alfa), and also with the specific procedure for surfactant administration in both treatment groups. Moreover, for baby randomized to the LISA group, causal relationship to CHF 6440 medical device will be also assessed.

An AE will be assessed as related to the medical device (i.e. CHF 6440 catheter) if associated with its technical features or with any defect/malfunction.

An AE will be assessed as related to the procedure (i.e. LISA or intubation, surfactant administration and brief ventilation) if connected with the technique, including user difficulties in applying it.

An AE can be assessed as related to multiple choices.

The expression “reasonable possibility of relatedness” is meant to convey, in general, that there are facts (evidence) or arguments meant to suggest a causal relationship.

The Investigator will be asked to consider the following before reaching a decision on causality assessment:

- Time relationship between study drug intake/device use/procedure for administration and event’s onset;
- Medical history;
- Lack of efficacy/worsening of existing condition;
- Study treatment(s);
- Mechanism of action of the study drug/device;
- Class effects of the study drug;
- Other treatments-concomitant or previous;
- Erroneous treatment with study medication (or concomitant)/device/procedure for

- administration;
- Protocol related process.

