For pharmacovigilance purposes, all SAEs should be followed-up in order to elucidate as completely and practically as possible their nature and/or causality until resolution of all queries, clinical recovery is complete, laboratory results have returned to normal, stable condition is reached or until the subject is lost to follow-up. Follow-up may therefore continue after the subject has left the study. In this case, the follow-up will continue with no timelines for related SAEs, while for unrelated SAEs the type and extent of follow-up undertaken will be determined for each individual case and will depend upon the nature (e.g. events with poor prognosis or which do not resolve), severity and medical significance of the event.

AEs related to the procedure for surfactant administration

The procedure for surfactant administration will last from the application of the laryngoscope up to the removal of the CHF 6440 catheter in the LISA treatment group or the ETT in the comparator arm within one hour after the instillation of poractant alfa.

All AEs during procedures for surfactant administration will be carefully monitored and recorded in both arms. Specific focus will have to be paid on the following AEs:

- Obstruction of the CHF 6440 catheter or ETT;
- Bradycardia;
- Neonatal oxygen desaturation;

- Apnoea;
- Hypotension requiring treatment;
- Any episodes of cough, sneezing, choking, laryngospasm, surfactant reflux, vomiting.

A complete qualitative risk assessment has been conducted to identify and mitigate potential safety risks associated with use of CHF 6440 medical device. The results provide evidence that the benefits of using the device outweigh the residual risks and do not highlight any specific additional risk or safety issue than the ones listed above.

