12.3.5. Safety variables

Adverse Events and Neonatal Morbidities

- Number and percent of neonates reporting AEs started during procedure for surfactant administration as well as AEs started during the procedure and judged related to the procedure will be summarized by treatment group.

For LISA group, any AE assessed as related to CHF 6440 catheter will be considered procedure-related.

These events will be also summarized by treatment group based on action required, if any (i.e. supplementary oxygen or transient increase in FiO₂, manual positive pressure ventilation, endotracheal intubation, administration of, crystalloids, or cardiopulmonary resuscitation or administration of adrenaline). The duration of endotracheal intubation and positive pressure ventilation will be

summarized as well.

A subgroup analysis of AEs during procedure for surfactant administration will be performed based on the use of sedation and/or analgesia (Yes/No).

- Incidence of AEs including neonatal complications of prematurity (see [APPENDIX III](#) for complete list), related AEs (ADRs), serious AEs (SAEs) and AEs leading to death will be summarized by treatment group both in term of frequency of neonates with at least one AE and in term of frequency of AEs (number of events). All the aforementioned categories of AEs will be summarized by System organ Class (SOC) and Preferred Term (PT).
- Frequency of neonates with major neonatal morbidities at discharge or 40 weeks PMA (whichever comes first) will be summarized by treatment group.

Vital Sign

- Vital signs parameters (SBP, DBP MBP, HR and RR) will be summarized as absolute and the change from baseline (pre-procedure) by treatment group using descriptive statistics.

Pain assessment

- PIPP score will be summarized by treatment group by means of descriptive statistics.

First administration

- Number of 1st failed attempt to insert the catheter/ETT will be summarized by treatment group. Percentage of neonates with 1st failed attempt will be compared between group using the Cochran-Mantel-Haenszel adjusted for gestational age group. The CMH adjusted difference with its 95% CI will be presented.
- Number of attempts to the first successful insertion will be summarized by treatment group by means of descriptive statistics.
- Number of device misallocation (i.e., esophageal intubation) will be summarized by treatment group by means of descriptive statistics.

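### Procedure relatedness is judged for every adverse event but summarised only for events that start before the catheter or tube is removed, a cut-off that falls at different times in the two arms

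*Protocol*

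**What the plan says.** Section 10.8 records AEs from the beginning of the procedure until the subject's participation ends. Section 10.4 has each one assessed against poractant alfa, "and also with the specific procedure for surfactant administration in both treatment groups", and in the LISA group against CHF 6440 as well. It sets no time limit on these judgements and allows an AE to be related to more than one of them.

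The summaries are narrower. Section 9 lists "Number and percentage of neonates with AEs starting during overall procedure for surfactant administration judged related to the procedure". Section 12.3.5 repeats the restriction: "AEs started during the procedure and judged related to the procedure will be summarized by treatment group". The Protocol Outline does the same. Within the same bullet, Section 12.3.5 merges device relatedness into procedure relatedness: "For LISA group, any AE assessed as related to CHF 6440 catheter will be considered procedure-related".

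Section 10.8 defines the window: "The procedure for surfactant administration will last from the application of the laryngoscope up to the removal of the CHF 6440 catheter" in LISA, or removal of the ETT, within one hour of instillation, in the comparator arm.

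For the whole study, Section 12.3.5 plans all AEs including complications of prematurity, and then "related AEs (ADRs), serious AEs (SAEs) and AEs leading to death will be summarized by treatment group". Section 10.1 defines an adverse drug reaction (ADR) through "responses to an investigational medicinal product related to any dose administered".

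**The concern.** Both arms receive poractant alfa at the same doses (Section 6.2.2), so what is randomised is the technique and the delivery device. The main objective (Section 2.1) is the short-term and mid-term safety of one technique against the other. Yet the only relatedness table open to late onset concerns the product common to both arms, while the relatedness summary for the randomised contrast stops at device removal. Investigators will make the procedure judgement for later events, and the plan gives that judgement no place in the results.

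At stake is a table that readers will take as the trial's count of procedure-related harm. It covers only part of the period over which that judgement is made, and a different part in each arm.

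**Working it through.** No alpha, power or rate enters this point, and the protocol gives no figure to reproduce. The check is to trace each causality judgement in Section 10.4, by onset before or after removal (Section 10.8), to the relatedness summaries in Sections 9 and 12.3.5.

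| Judged related to | Starts before removal | Starts after removal |
|---|---|---|
| Drug only | ADR table | ADR table |
| Drug and procedure | ADR table and procedure-related summary | ADR table only, so shown as drug-related |
| Procedure only | Procedure-related summary | No relatedness summary |
| CHF 6440 only (LISA) | Procedure-related summary | None, or ADR table, depending on how Section 10.1 is read |

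An AE in any cell also enters the all-AE tables by arm and, where it qualifies, the serious-AE, fatal-AE and complications-of-prematurity tables.

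*The certain gap* is the procedure-only, late-onset cell.

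*The ambiguous cell* is late, device-only AEs. The first definition in Section 10.1 refers to a medicinal product. The sentence that follows it admits AEs with a reasonable causal relationship to an investigational product, and Section 10.2 judges expectedness against an Investigator's Brochure for both poractant alfa and the catheter. The catheter might therefore be read in. That reading creates an imbalance of its own: device causality is assessed only in LISA (Section 10.4), and control tubes are site stock (Section 6.5). Late device-related events would then be counted as related in LISA, while late events due to intubation in the control arm would not.

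*The cut-off in each arm*, measured from the end of instillation:

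- LISA: instillation takes 0.5-3 minutes and the catheter is removed once surfactant is given (Section 6.2.3.3). The window closes at, or very soon after, the end of instillation.
- ETT: the neonate may be extubated at once, or ventilated and extubated within one hour (Section 6.2.3.4). The window closes anywhere from about 0 to 60 minutes after instillation.

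Take an apnoea 20 minutes after instillation, judged related to the procedure. It is in the summary for a control neonate who is still intubated, and out of it for any LISA neonate whose catheter was removed after dosing.

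*One line that might close the gap* is the Outline's sedation subgroup, which names surfactant- and procedure-related AEs without a time limit. It sits under the during-procedure bullet, and Section 12.3.5 words the same subgroup as AEs during the procedure. It does not supply an any-onset table, and the two wordings differ.

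**The case against.** The strongest reply is that the randomised comparison does not need attribution. The drug is the same in both arms, so the all-AE, serious-AE, fatal-AE and complications tables by arm already estimate the effect of technique and device, whatever the investigator believed about cause. Bronchopulmonary dysplasia, death or bronchopulmonary dysplasia, and mortality are compared by CMH test as well. In an open-label trial of neonates with many comorbidities, attributing late events is subjective, so confining the label to peri-procedural events is defensible. This largely stands. It is why the point is moderate, and why the added tables should be read beside the all-cause ones. It does not explain why a judgement required for every AE should be reported for only some of them.

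A reader might infer that delayed harms such as air leak or pulmonary haemorrhage disappear from the results. The documents do not support that. Both are in Appendix III, must be recorded as AEs, and are summarised by arm. Only the attribution is missing.

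It can also be said that control intubation is part of the control procedure, so a longer window there is correct. As a count of AEs during the procedure, that is fair. As the only measure of procedure-related AEs, it gives the arms unequal observation after dosing.

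Finally, further relatedness tables are ordinary SAP content, and the SAP is not shown. It may add them. But the protocol itself fixes the onset restriction and equates related AEs with ADRs, so the correction belongs in the protocol.

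**Conclusion.** The point holds in a limited form. AEs that start after removal and are judged related to the procedure alone are counted by arm but never reported as procedure-related. Late device-only AEs are in doubt. The cut-off differs between arms by up to about one hour after instillation, which can make procedure-related AEs look less frequent in LISA relative to control.

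This rests on reading related AEs (ADRs) as drug-related, following the definition in Section 10.1. If the sponsor meant relatedness to drug, procedure or device, late events would enter that table, but the table would then pool drug and procedure and still not isolate the randomised contrast.

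The documents give no frequency of procedure-related AEs by time of onset, so the number mislabelled cannot be estimated. One might go further and conclude that the report will understate the harm of LISA as a whole. That does not follow, because the all-cause comparisons by arm remain intact. Severity is moderate: no data are lost and the remedy is cheap, but it touches the main objective.

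**What to change.** In Sections 9 and 12.3.5 and in the Protocol Outline:

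1. Add the number and percentage of neonates with at least one AE judged related to the administration procedure, whatever the time of onset, by treatment group, SOC and PT. In LISA, include AEs judged related to CHF 6440.
2. Add the same summary for serious AEs.
3. Keep the during-procedure count as a labelled subset of the first summary.
4. State whether related AEs (ADRs) means drug-related only, and whether the catheter counts as an investigational product for that table.
5. Reconcile the wording of the sedation subgroup between the Outline and Section 12.3.5.

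The cost is a few extra tables and some clarifying sentences. The causality data are already collected for every AE, and no visit, assessment or treatment changes. The report should say that attribution of late events is unblinded and subjective, and present these tables alongside the all-cause ones.

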Reference product dose/route/regimen	
As standard control treatment, neonates spontaneously breathing and stabilized on NIV will be intubated with an endotracheal tube to receive poractant alfa 200 mg/kg under invasive ventilation.

	
Poractant alfa will be instilled according to the approved endotracheal method of administration, connecting the syringe filled with poractant alfa suspension to either:
 
 • a 5-French end-hole catheter inserted into the ETT or • the proximal end of the secondary lumen of a dual lumen ETT. 
After administration, manual ventilation could be continued, or the neonate could be connected to the ventilator, or the neonate could be immediately extubated and placed again on NIV. If connected to the ventilator, extubation should be performed within one hour after surfactant administration and then the neonate placed again on NIV.

Number of subjects	One hundred (100) randomized neonates to LISA treatment group, fifty (50) randomized neonates to conventional surfactant administration group (150 neonates in total)
Study population	Preterm neonates with early clinical signs of RDS
Inclusion/exclusion criteria	
Inclusion Criteria
 
Subjects must meet all the following inclusion criteria to be eligible for enrollment into the study:
 
 1. Written informed consent obtained by parents/legal representative (according to local regulation) prior to or after birth; 2. Preterm neonates of either sex aged ≥ 30 minutes and < 24 hours, spontaneously breathing and stabilized on NIV; 3. Gestational age of 25^{+0} weeks up to 28^{+6} completed weeks; enrollment will be restricted to subjects aged 27^{+0} weeks up to 28^{+6} GA weeks until safety evaluation of first 15 subjects is completed; 4. Clinical course consistent with RDS; 5. $FiO_2 \geq 0.30$ to maintain preductal SpO_2 in the target range of 88–95%.
Inclusion/exclusion criteria	
Exclusion Criteria
 
The presence of any of the following will exclude a subject from the study enrollment:
 
 1. Need for immediate endotracheal intubation for cardiopulmonary resuscitation or insufficient respiratory drive; 2. Use of nasal high frequency oscillatory ventilation (nHFOV)

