6.2.3.4 Conventional Intubation, surfactant administration and brief ventilation

As standard control treatment, neonates spontaneously breathing and stabilized on NIV will receive surfactant via ETT using an approved method of administration, connecting the syringe filled with poractant alfa suspension to:

- a 5-French end-hole catheter inserted into the ETT
or
- the proximal end of the secondary lumen of a dual lumen ETT.

The standard ETT has markings along the side to help identifying the correct distance from the tip of the tube.

Following direct laryngoscopy, the ETT will be inserted through the vocal cords into the trachea to the desired depth. The laryngoscope will be then carefully removed. The correct ETT position into the trachea will be confirmed by the visualization of tip depth markings and by the tip-to-lip measurement. The tube position could be checked by auscultation of the chest to ensure equal aeration of both lungs, observation of chest movement synchronous with positive pressure inflation, enhancement of vital signs, absence of stomach distension while ventilation, and where possible, with the measurement of end tidal CO₂ by colorimetric system on the ETT. Once the tube position is confirmed, the ETT will be secured with adhesive tape or other ways according to the NICU policy.

After administration, manual ventilation can be continued, or the neonate can be connected to the ventilator, or the neonate can be immediately extubated and placed again on NIV. Do not suction airways for 1 hour after surfactant instillation unless signs of significant airway obstruction occur.

If connected to the ventilator, extubation should be performed within one hour after surfactant administration and then the neonate placed again on NIV.

Details of the procedure as well as neonate's vital signs and any occurring adverse event will be recorded according to the time points of the protocol by the team member assisting or observing the procedure.

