8. EFFICACY ASSESSMENTS

The following variables will be used to describe the efficacy of the two procedures:

- Percentage of neonates needing invasive mechanical ventilation (MV) in the first 72 hours of life, 28 days PNA and within 36 weeks PMA defined as follows:

ETT group

- neonates not extubated within 1 hour from initial surfactant administration and receiving MV for more than 1 hour;
- neonates extubated and re-intubated to receive MV of any duration.

LISA group

- neonates intubated to receive MV of any duration,
 - Duration of invasive ventilation (hours) in the first 72 hours of life, 28 days PNA and within 36 weeks PMA;
 - Percentage of neonates needing any intubation procedure, outside the initial surfactant administration period, in the first 72 hours of life, in the first 28 days PNA and within 36 weeks PMA;
 - SpO₂ at time 0 (study treatment administration), 5, 15, 30 minutes, at 1, 6, 12, 24, 48, 72 and 120 hours post treatment; additionally, at 28 days PNA and at 36 weeks PMA for neonates still receiving any form of respiratory support;
 - FiO₂ at time 0 (study treatment administration), 5, 15, 30 minutes, at 1, 6, 12, 24, 48, 72 and 120 hours post treatment; additionally, at 28 days PNA and at 36 weeks PMA for neonates still receiving any form of respiratory

support;

- SpO₂/FiO₂ at time 0 (study treatment administration), 5, 15, 30 minutes, at 1, 6, 12, 24, 48, 72 and 120 hours post treatment; additionally, at 28 days PNA and at 36 weeks PMA for neonates still receiving any form of respiratory support;
- Percentage of neonates needing additional surfactant doses and number of surfactant doses;
- Duration of oxygen alone supplementation (days) and any non-invasive ventilation during the study (days);
- Blood gas analysis, specifically acid-base balance parameters (i.e. pH, pCO₂, pO₂, HCO₃, BE, lactate) pre-surfactant administration (when applicable), at 1 hour, 6 hours, 24, 48 and 72 hours after study treatment.

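### The procedural AE rows for bag-and-mask ventilation and endotracheal intubation are not like-for-like between arms, and escalation through a tube already in place has no row

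*Protocol*

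**What the plan says.** Section 9 lists the variables for the period of surfactant administration. After two overall incidence variables, it counts AEs by the action they required. The respiratory rows are:

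- oxygen or a rise in FiO2, provided no step-up of invasive or non-invasive ventilator support was needed;
- AEs "requiring administration of manual (bag and mask) pressure positive ventilation and related duration of ventilation", labelled as non-invasive ventilation;
- the "Number of AEs starting during overall procedures for surfactant administration requiring endotracheal intubation and related duration of intubation (invasive ventilation").

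The same wording serves both arms. Section 12.3.5 then states: "These events will be also summarized by treatment group based on action required, if any".

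In the control arm, the Protocol Outline (reference product) says that "neonates spontaneously breathing and stabilized on NIV will be intubated with an endotracheal tube to receive poractant alfa 200 mg/kg under invasive ventilation". Section 6.2.3.4 adds: "After administration, manual ventilation can be continued, or the neonate can be connected to the ventilator", with immediate extubation as the third possibility. Section 10.8 starts the procedure at laryngoscope application and ends it "up to the removal of the CHF 6440 catheter in the LISA treatment group or the ETT in the comparator arm within one hour" of instillation.

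For the efficacy variable on need for mechanical ventilation, Section 8 does separate the arms. A control neonate counts only under rules such as "neonates not extubated within 1 hour from initial surfactant administration and receiving MV for more than 1 hour", or on re-intubation; a LISA neonate counts on any intubation for ventilation.

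**The concern.** A row defined by a rescue action compares two arms fairly only if the action is equally available as a rescue in both. Here it is not. A LISA neonate is on NIV without a tube, so an apnea or desaturation can lead to mask PPV or intubation and be counted. A control neonate with the tube in place already has the support that defines both rows.

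Procedural AEs come first in the list of safety measures under the main objective (Section 2.1). A reader who sets the two arms side by side could take a difference in definition for a difference in how well the neonates tolerated the procedure. The duration attached to the intubation row has the same weakness: in control, nothing separates planned tube time from time caused by an AE.

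**Working it through.** **1. Where each response is counted under Section 9**

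| Response to the AE | LISA neonate | Control neonate with tube in place |
|---|---|---|
| Oxygen or FiO2 only | FiO2 row | FiO2 row |
| Bag and mask | Mask row | Only before placement, between attempts or after removal |
| More support through the existing tube | Does not arise before intubation | No respiratory row |
| Tube inserted because of the AE | Intubation row | Only as replacement or re-intubation |

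The third line is the gap. The FiO2 row excludes any step-up of invasive support, so the event does not fall into the milder row; it falls into none. The same exclusion leaves an increase of support on the NIV device without a row in LISA.

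**2. Wording across sections.** Section 9 specifies bag and mask. The action list in Section 10.6 and the summary in Section 12.3.5 refer to manual positive-pressure ventilation with no interface. One site could record bagging through the tube as that action while another, following Section 9, does not. Section 10.6 also pairs endotracheal intubation with invasive ventilation in one option and offers none for increased support through a tube already in place.

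**3. Counts and allocation.** Section 12.1 gives 150 neonates at 2:1: 150 × 2/3 = 100 LISA and 150 × 1/3 = 50 control, as stated. Section 9 defines the action rows as numbers of AEs, without percentages. At an equal risk of 20%, and at most one event per neonate, the expected counts are already 20 and 10.

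**4. Illustration of possible size.** The protocol gives no event rates, so these inputs are assumptions:

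- p = risk, equal in both arms, of an event that would need mask PPV or intubation in a neonate without a tube;
- f = share of such control events that can still enter the two rows;
- at most one event per neonate.

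Expected counts are 100p in LISA and 50pf in control. The apparent difference in percentages is p(1 − f).

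| p | f | LISA | Control | Difference | Chance of Fisher p < 0.05 |
|---|---|---|---|---|---|
| 10% | 1 | 10/100 | 5/50 | 0 points | 3.3% |
| 10% | 0.5 | 10/100 | 2.5/50 | 5 points | 11% |
| 10% | 0.25 | 10/100 | 1.25/50 | 7.5 points | 27% |
| 20% | 1 | 20/100 | 10/50 | 0 points | 4.0% |
| 20% | 0.5 | 20/100 | 5/50 | 10 points | 31% |
| 20% | 0.25 | 20/100 | 2.5/50 | 15 points | 72% |
| 30% | 1 | 30/100 | 15/50 | 0 points | 4.0% |
| 30% | 0.5 | 30/100 | 7.5/50 | 15 points | 50% |
| 30% | 0.25 | 30/100 | 3.75/50 | 22.5 points | 92% |

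The last column, enumerated exactly from two binomials, only gauges how striking the table would look. The protocol plans no test on these rows.

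**5. Why the direction is open.** Section 6.2.3.3 has the LISA catheter removed once surfactant has been instilled over 0.5 to 3 minutes. The control window can run to one hour after instillation. If the longer window multiplies the control risk by r, the control percentage becomes p × r × f, which equals the LISA percentage when r × f = 1: r = 2 at f = 0.5, r = 4 at f = 0.25. Sites that code bagging through the tube as manual ventilation would raise the control count further.

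**The case against.** A reader might infer that these rows count against LISA alone, that control will show near-zero counts, or that control events are downgraded to the mild row. The documents support none of these.

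- Control neonates can enter both rows: during laryngoscopy, between failed attempts, through tube obstruction (an AE of specific focus in Section 10.8) or misplacement needing a new tube, or through an AE that starts in the window and leads to re-intubation. Section 6.2.3.5 begins resuscitation with PPV in both arms.
- AE intensity is graded separately (Section 10.3), so these rows do not make events severe or mild.
- The two overall procedural AE variables in Section 9 count neonates whatever the action.
- The rows are summarised, not tested, in a study that Section 1.1 calls explorative.
- Conversion to intubation during LISA is a genuine safety outcome and deserves its own row.

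All of this stands, and it limits the point to the descriptive action categories. It can also be said that derivation rules belong in the SAP, which is not at hand. That answers less: the definitions and the action list are set in the protocol, they disagree on the interface, and an action with no option of its own in the list cannot be reliably recovered at analysis.

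**Conclusion.** The mask-PPV and intubation rows are not comparable between arms, because the actions that define them are part of the control procedure for most of its window. Support increased through an existing tube has no respiratory row, and Sections 9, 10.6 and 12.3.5 differ in wording. Section 8 shows that the protocol handles the same asymmetry for need for mechanical ventilation; no such rule is given for the safety rows.

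The net size and direction of the bias are not fixed by the document. Under equal risks of 10% to 30%, with a quarter to half of control events codable, the apparent LISA excess would be 5 to 22.5 points. Those inputs are assumptions, and the longer control window or looser coding could offset or reverse the excess. No formal test and no overall AE incidence is affected. This is worth correcting because it concerns the reading of a main-objective safety measure and the remedy is cheap.

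**What to change.** 1. Keep the existing rows, including conversion to intubation.
2. Section 10.6: add the action *increase in ventilatory support via existing ETT*. The same entry can note an increase on the NIV device, so that the new row below covers every interface.
3. Sections 9 and 12.3.5: add an arm-neutral row, *AEs requiring escalation of positive-pressure support beyond the assigned procedure, by any interface, or unplanned intubation, re-intubation or tube replacement*, with arm-specific rules in the manner of Section 8. Base the between-arm comparison on this row.
4. Align Sections 9, 10.6 and 12.3.5 on whether manual ventilation means bag and mask only or includes bagging through the tube.
5. Report the number and percentage of neonates beside the event counts, given the 2:1 allocation.

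The cost is one extra eCRF option, one extra table row and short wording changes. Only recording and tabulation change; the management of the neonates does not.
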